Subjects are ineligible for the study if they meet any of the following criteria:

1. Subject is from a vulnerable population, as defined by the US CFR Title 45, Part 46, Section 46.111(b) and other local and national regulations, including but not limited to, employees (temporary, part-time, full time, etc) or a family member of the research staff conducting the study, or of the sponsor, or of the clinical research organization, or of the IRB/IEC.

2. Subject is unwilling to receive, or is intolerant of, SC injections.
3. Subject has a history of sensitivity to ACTH preparations or sensitivity to porcine protein products.
4. Any difference >10% in FVC on spirometry between the determination at Screening (Visit 1) and the determination at Visit 2.
5. Pulmonary arterial hypertension requiring or receiving treatment.
6. Extra pulmonary involvement that per the Investigator's evaluation requires treatment that would impede corticosteroid tapering for pulmonary involvement.
7. Treatment with antitumor necrosis factor- α antibody (eg, infliximab, adalimumab) in prior 3 months.
8. Subject has any known contraindication(s) to Acthar Gel including, but not limited to:
 - Any known history of:
 - Scleroderma
 - Osteoporosis (evidence of vertebral or long bone fracture, or a lumbar T-score of more than -2.5 SD below the mean of the reference population). Subjects previously diagnosed as having osteoporosis and successfully treated will not be excluded solely on the basis of a historical diagnosis of osteoporosis as long as the lumbar T-score obtained per routine follow up within the 12 months prior to Screening (Visit1) is \geq -2.5 SD.
 - Ocular herpes simplex
 - Any primary adrenocortical insufficiency or adrenal cortical hyperfunction.
 - Any current congestive heart failure (defined as New York Heart Association Functional Class III to IV).
 - Peptic ulcer requiring treatment or history of upper gastrointestinal bleeding within 24 weeks prior to Screening (Visit 1).
 - Recent major surgery (ie, major fluid or blood shift) within 24 weeks prior to Screening (Visit 1).
9. Subject has uncontrolled diabetes, hypertension, or other contra-indication to increased dosage of glucocorticoids.
10. Subject has chronic active hepatitis including active or chronic hepatitis B, or acute or chronic hepatitis C.
11. Subject has a history of TB infection, any signs/symptoms of TB, or any close contact with an individual with an active TB infection.

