7.2.2. Pulmonary Function Tests

PFTs are routinely used in the evaluation of pulmonary sarcoidosis patients. However, there is no diagnostic pattern in PFTs. The most prevalent pattern of PFTs is restrictive lung disease, although obstruction can nevertheless also be present, either in isolation or concomitantly. FVC is most commonly used to measure response to therapy. Nonetheless, the volume of FVC does not correlate clinically with symptoms of dyspnea, and there is no definite consensus on how to follow changes in FVC in response to treatment. Based on intrapulmonary fibrosis, in the absence of better data, a decline of $\geq 5\%$ (absolute change of predicted) FVC is consistent with refractoriness in sarcoidosis patients (Korsten et al., 2016; Baughman et al., 2015).

Diffuse lung capacity of carbon monoxide has also been used. However, there is a higher intra-subject variability than FVC. Significant reduction in DLCO may indicate refractory pulmonary disease in the absence of pulmonary arterial hypertension as a cause of drop in DLCO ([Korsten et al., 2016](#); [Baughman et al., 2015](#)).

PFT will follow ATS/European Respiratory Society task force for standardization of lung function testing ([Miller et al., 2005](#)) and the revisions provided for DLCO ([Graham et al., 2017](#)).

PFT results will include FEV1, FVC, FVC % predicted (NHANES III reference values), FEV1/FVC ratio, PEFR or FEF_{max}, TLC, RV, DLCO (uncorrected for Hb), DLCO % predicted and DLCO/VA at screening visit, Visits 5, 8, 10, and 11 (every 12 weeks).

At the randomization visit, spirometry results will include FEV1, FVC, FVC % predicted (NHANES III reference values), FEV₁/FVC ratio and PEFR or FEF_{max}.

Patients should be instructed to avoid smoking within at least 1 hour of testing, consuming alcohol within 4 hours of testing, performing vigorous exercise within 30 minutes of testing, wearing clothing that substantially restricts full chest and abdominal expansion, and eating a large meal within 2 hours of testing. Ideally, when patients return for repeat testing, the equipment and the operator should be the same, and the time of day should be within 2 hours of previous test times. The order of the tests should be kept constant for each subject on each subsequent PFT.

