11.1. Study Days -28 to -1 (Screening Visit 1)

Screening assessments must be performed within 28 days prior to Visit 2.

The following procedures will be performed at the screening visit:

- Informed consent. Neutral language should be used in describing the study to neutralized placebo effect.
- Injection and diary training. Subjects (or caregivers) will be trained on SC injections and diary completion using the training tools provided separately. The injection training may be foregone if either the subject or caregiver is a medically trained professional.
- Inclusion/exclusion criteria.
- Medical, surgical, and medication history. Medical history will include smoking history (classified into 1 the following categories: current smoker; ever smoked [more than 1 cigarette/day for more than 1 year]; never smoked), length of sarcoidosis diagnosis, organ involvement, and prior and current medication. Occupational history should also be collected.
- Demographics.
- Concomitant medications.
- Height.
- Vital signs. Vital signs will be obtained after the subject has been seated for 5 minutes (minimum) and will include systolic and diastolic blood pressures, pulse rate, and respiratory rate.
- Weight measured. Every effort should be made for weight to be measured by the same calibrated scale at every visit.
- Physical examination (see [Section 14.3](#)). The full physical examination will include a targeted examination of the organ(s) involved. All efforts must be undertaken for the same physician to perform the physical examination per subject, per organ involved, at each visit.

- Physician Global Assessment ([Attachment 7](#))
- ePOST.
- 12-Lead ECG (see [Section 14.6](#)).
- Patient-reported outcomes and assessments. Patient-reported outcomes include: Steroid toxicity questionnaire; King's Sarcoidosis Questionnaire ([Attachment 4](#)); Fatigue Assessment Scale ([Attachment 5](#)); Patient's Global Assessment ([Attachment 6](#)); Medical Research Council Dyspnea Scale ([Attachment 8](#)); Leicester Cough Questionnaire ([Attachment 9](#)), WPAI ([Attachment 10](#)) Prior to filling out any patient-reported outcomes at Visit 1, training will be provided as to the nature, purpose, and best way of filling these out. For example, reading the last question of the Fatigue Assessment Scale carefully.
- 6MWT: The 6MWT would be performed according to the ATS protocol ([Attachment 12](#)). Reasons for not performing the 6MWT will be captured in the eCRF.

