11.2. Visit 2 Procedures

The investigator or designee will complete the following procedures at Visit 2:

- Inclusion/exclusion criteria review.
- Spirometry (ascertain any difference in FVC < 10% compared with FVC performed at Visit 1 before continuing).
- Vital sign determinations Vital signs will be obtained after the subject has been seated for 5 minutes (minimum) and will include systolic and diastolic blood pressures, pulse rate, and respiratory rate (see [Section 14.4](#)).
- Weight measured. Every effort should be made for weight to be measured by the same calibrated scale at every visit.
- Physical examination (see [Section 14.3](#)). The full physical examination will include a targeted examination of the organ involved. All efforts must be undertaken for the same physician to perform the physical examination (per organ involved) at each visit.
- ePOST: All efforts must be undertaken for the same physician to perform the ePOST ([Attachment 3](#)) side-by-side with prior evaluations.
- Physician Global Assessment ([Attachment 7](#)).
- Patient reported outcomes and assessments. Patient-reported outcomes include: Steroid toxicity questionnaire; King's Sarcoidosis Questionnaire ([Attachment 4](#)); Fatigue Assessment Scale ([Attachment 5](#)); Patient's Global Assessment ([Attachment 6](#)); Medical Research Council Dyspnea Scale ([Attachment 8](#)); Leicester Cough Questionnaire ([Attachment 9](#)), WPAI ([Attachment 10](#)).
- Clinical laboratory tests:
 - Complete blood count.
 - Clinical chemistry including liver function tests (samples will be collected from subjects who have been fasted for at least 12 hours. Drinking water is allowed).
 - HbA1C.
 - Human chorionic hormone (urine pregnancy testing, females of child bearing potential only [performed at a local laboratory]).
- Injection and diary training (if additional training is required).
- Contact IXRS to randomize subject and dispense study drug kits.
- Dosing will begin after Visit 2 procedures are completed and subject is randomized. Subjects (and/or caregivers) will be trained on SC injections and diary

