Clarification for “daily” prednisone	Section 10.1 Inclusion Criteria #9	9. Subject receiving ≥ 5 mg and ≤ 40 mg prednisone (or equivalent) for pulmonary sarcoidosis.	9. Subject receiving ≥ 5 mg and ≤ 40 mg daily prednisone (or equivalent) for pulmonary sarcoidosis.

Rationale	Location	Original	Revisions/Additions in Bold
Allowing subjects whose FVC is higher than 95% predicted at screening and can potentially show improvement in FVC.	Section 10.1 Inclusion Criteria #12	12. Forced vital capacity (FVC) $\geq 45\% \leq 95\%$ predicted.	12. Forced vital capacity (FVC) $\geq 45\%$ predicted. If FVC at Screening is more than 95% predicted, a documented decrease $\geq 5\%$ absolute change of % predicted in the best available FVC is required after diagnosis of Sarcoidosis.
Excluding subjects with prior history of Sarcoidosis treatment with Acthar	Section 10.2 Exclusion Criteria #8	Not available	Subject has any history of use of ACTH preparations for treatment of Sarcoidosis.
Address missed procedures and visits	Section 12 PROCEDURES	The schedule of study procedures is summarized in the Schedule of Events (Table 1).	
The schedule of study procedures is summarized in the Schedule of Events (Table 1). If the subject is unable to come to the study site for any visit after the Baseline visit, all procedures that can be completed remotely (eg, by telephone) will be conducted as scheduled.
 
Collect as much information as possible, including but not limited to, AE information, new concomitant medications and changes in existing therapy, corticosteroid use, compliance with investigational therapy. Complete applicable physician assessments, PFT tests, subject reported outcomes and assessments, 6MWT, ECG, imaging and laboratory tests at the next planned study visit as unscheduled procedures, if not

Rationale	Location	Original	Revisions/Additions in Bold
			already scheduled for that particular study visit. Changes in study visit schedule, missed visits, and procedures will be captured in the eCRF.
Addition of WPAI, a questionnaire to assess HEOR outcomes	Synopsis, Efficacy Evaluation	Not Available	11. WPAI.

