- Two baselines, baseline of overall study and baseline of active treatment, have been defined. Baseline of overall study is defined as the last assessment prior to the first dose of IMP at the double-blind treatment phase. Baseline of active treatment is defined as the last assessment prior to the first dose of active treatment in either the double-blind treatment phase or the open-label extension phase. All the analysis in the open-label extension phase that involves presenting change and/or percent change from baseline will present change/percent change from both baselines.
- Summary statistics will be provided for all study variables with descriptive statistics (number of subjects, mean, standard deviation (SD), median, minimum,

and maximum) for numerical (or continuous) variables. Frequency and percentages will be calculated for categorical variables.

- Unless specified otherwise for a given analysis, all statistical tests, when applicable, will be 2-sided with a significance level of 0.05.
- All data collected will be presented in listings, sorted by treatment group, subject identifier and date/time of procedure or event, if applicable.

All analyses will be conducted using SAS® Version 9.4 or higher. The Medical Dictionary for Regulatory Activities (MedDRA) version 23.0 will be used for coding adverse events (AEs), and medical and surgical histories. Prior or concomitant medication data will be coded according to the Anatomical Therapeutic Chemical (ATC) coding scheme of the World Health Organization (WHO) Drug Dictionary (Enhanced B2 dated March 2018 version, or higher) level 2 term.

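### FVC, KSQ and FAS each have two pre-dose values but the SAP baseline keeps only the last; averaging the two is a cheap gain in precision, not the repair of an error or a bias

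*SAP*

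**What the plan says.** **Baseline.** SAP 4.3: "Baseline of overall study is defined as the last assessment prior to the first dose of IMP at the double-blind treatment phase". SAP 9.1 defines no separate baseline for the STS, and its only STS sensitivity analysis uses observed data.

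**Pre-dose measurements.** Protocol 7.2.2 schedules the full PFT, including FVC, at screening and then at "DLCO % predicted and DLCO/VA at screening visit, Visits 5, 8, 10, and 11 (every 12 weeks". It adds: "At the randomization visit, spirometry results will include FEV1, FVC, FVC % predicted (NHANES III reference values". Protocol 11.1 and 11.2 schedule KSQ and FAS at both visits. Visit 2 values are pre-dose: "Dosing will begin after Visit 2 procedures are completed and subject is randomized". DLCO and HRCT have one scheduled pre-dose measurement, at screening.

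**Scoring.** In SAP 9.1, Table 1, FVC scores +1 or -1 at a change of 5 absolute points of % predicted; KSQ General Health and FAS score at 4 points.

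**Entry tolerance for FVC.** Exclusion 4 removes a subject for "Any difference >10% in FVC on spirometry between the determination at Screening (Visit 1) and the determination at Visit 2". The Visit 2 procedures say: "Spirometry (ascertain any difference in FVC < 10% compared with FVC performed at Visit 1 before continuing". Neither states whether the 10% is relative or in points of % predicted. Inclusion criteria 8 and 12 do specify "absolute change of % predicted".

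**The concern.** Each FVC, KSQ or FAS change carries the error of a single baseline reading although a second reading is already scheduled. STS items are cut at fixed thresholds with no baseline adjustment, and SAP 9.3 and 9.5 compare changes by two-sample t-tests, so that error enters in full. Stable subjects are then scored Improved or Deteriorated in both arms, which tends to blur a treatment difference. The entry rule does not prevent this for FVC, because it tolerates a pre-dose gap that is usually wider than the scoring cut. No entry rule limits the pre-dose gap for KSQ or FAS.

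The same changes feed three of the six primary outcome measures in Protocol 7.4 and the FVC improvement rates in SAP 9.3. SAP 4.1 reports 55 randomized subjects and no sample size calculation, so there is little precision to spare.

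**Working it through.** The plan states no figure to reproduce here. The documents supply the visit schedule, the thresholds and the 10% rule; the within-subject SD is assumed.

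**1. Tolerated FVC gap against the 5-point cut.** If the 10% is absolute, the gap is 10 points for everyone, twice the cut. If it is relative to Visit 1, the gap is 0.10 x FVC % predicted:

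| FVC % predicted | Relative gap (points) |
|---|---|
| 45 (entry minimum) | 4.5 |
| 50 | 5.0 |
| 60 | 6.0 |
| 80 | 8.0 |
| 95 | 9.5 |

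On the relative reading the gap exceeds 5 points only above 50% predicted.

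**2. One subject.** Visit 1 = 80, Visit 2 = 73, Week 24 = 80. The pre-dose gap is 7/80 = 8.75%, which passes both wordings of the rule.
- Against Visit 2: 80 - 73 = +7, score +1.
- Against the mean, (80 + 73)/2 = 76.5: +3.5, score 0.
- Against Visit 1: 0, score 0.

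**3. Error variance of a change.** With independent errors of variance s² at each visit and before the entry exclusion:
- last value: s² + s² = 2s²
- mean of two: s² + s²/2 = 1.5s²

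The reduction is 0.5/2 = 25%, whatever the SD.

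**4. False scoring in a stable subject.** With normal errors and cut c, P(score not 0) is 2[1 - Φ(c/(s√2))] for the last value and 2[1 - Φ(c/(s√1.5))] for the mean. The FVC column with the exclusion comes from simulation (1,000,000 subjects per SD, true FVC 80, relative 10% rule). Each cell gives last value, then mean.

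| SD | FVC, cut 5, no exclusion | FVC, cut 5, with exclusion | KSQ or FAS, cut 4 |
|---|---|---|---|
| 2 | 7.7%, 4.1% | 7.6%, 4.1% | 15.7%, 10.2% |
| 3 | 23.9%, 17.4% | 22.4%, 17.4% | 34.6%, 27.6% |
| 4 | 37.7%, 30.7% | 34.7%, 30.8% | 48.0%, 41.4% |

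At SD 3 with the exclusion, about 19% of eligible subjects have pre-dose FVC values at least 5 points apart, and about 13.5% get a different FVC item score from the two baselines. The KSQ column is approximate because the score is stepped: in the SAP 15.2.2 table a rise of 4 points takes one raw point from totals 0-2 and 30-32, two from 3-8 and 22-29, and three from 9-21.

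**5. If true status drifts between Visits 1 and 2.** Let the true value move between these visits with variance d², independently of later change. The mean then adds d²/4 and saves 0.5s², so it remains better while d² < 2s². At s = 3 that allows a drift SD of up to 3√2 = 4.2 points within a screening window of at most 28 days.

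**6. Responder endpoint.** One item matters only next to the cut: a total of 1 without the steroid item is Non Response, while 2 is Partial Response and counts as a responder. Simulations of the six-item rule with 55 subjects give an indication only. One set assumed a 2.5-point benefit, true-change SD of 3 or 5, error SD of 2, 3 or 4, and illustrative steroid and HRCT shifts. Responder rates moved by at most 0.6 percentage points per arm, and power rose by 0.7 to 3.2 points (for example 0.64 to 0.66 at error SD 3 and true-change SD 5). A second set gave gains of about 1 to 5 points in all cases but one; with no spread in true change and error SD 2, power fell by about 4 points.

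**The case against.** The last pre-dose value is the usual convention, it is pre-specified, and it applies equally to both blinded arms. A reader might infer between-arm bias or an inflated type I error; the documents support neither. The choice is one of efficiency, and this objection stands.

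The effect on the responder endpoint is modest and can reverse, as step 6 shows. That stands too. So does the point that every probability rests on assumed SDs.

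The baseline noise is not unadjusted everywhere. The MMRM code in SAP 15.4 includes a baseline term, although the text of SAP 9.3 does not list one. The point therefore applies to the STS items, the improvement rates and the t-tests rather than to every FVC analysis.

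The two visits may not be exchangeable. Visit 1 can be 28 days earlier, KSQ recalls two weeks, and the FVC entry limits act on the screening value, so some regression to the mean is possible near those limits. Against this, questionnaire training comes before completion at Visit 1, prednisone must be stable before screening, tapering starts only at Visit 3, and no KSQ or FAS cut selects subjects. Step 5 shows that drift would have to be large to cancel the gain.

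Averaging also makes baselines differ in kind across STS items. They already differ in timing: FVC, KSQ and FAS use Visit 2, while DLCO and HRCT rest on screening.

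**Conclusion.** The point holds as a low-cost improvement. The SAP leaves a second pre-dose value unused for three of the six STS items. Averaging removes a quarter of the error variance in change (independent errors, before the exclusion) and lowers false FVC scoring in stable subjects from about 8, 22 and 35% to 4, 17 and 31% at assumed SDs of 2, 3 and 4. Misclassification is reduced, not eliminated. STS responder power should gain a few percentage points in most settings, without a guarantee.

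Two stronger inferences should be avoided. The tolerated FVC gap does not exceed the scoring cut for every subject: on the relative reading this fails from 45 to 50% predicted. Nor can a subject at exactly 10%, such as 80 then 72, be called eligible, since exclusion 4 would admit that subject and the Visit 2 wording would not.

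**What to change.** In SAP 4.3, define the overall-study baseline for FVC and FVC % predicted, KSQ and FAS as the mean of the Visit 1 and Visit 2 values, averaging KSQ after conversion to the 0-100 score. Specify that:
- if screening was repeated, the last valid Visit 1 value is used;
- if one visit is missing, the single available value is used;
- the same value serves as the active-treatment baseline for Acthar/Acthar subjects, so that the two baselines still coincide for them.

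Apply it in SAP 9.1, 9.3 and 9.5, and keep the last-value baseline as a sensitivity analysis. If treatment codes have already been seen, leave the last value as the main baseline and make the mean the sensitivity analysis.

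Separately, reconcile the >10% in exclusion 4 with the <10% in the Visit 2 procedures, and state whether the 10% is relative or absolute.

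The cost is SAP wording and reprogramming of the baseline derivation and the analyses that use it; no new data are needed. The downsides are a departure from the usual last-value convention, and that DLCO and HRCT keep a single screening baseline.

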4.4. Analysis Populations

4.4.1. Modified Intent-to-Treat Population

The modified Intent-to-Treat (mITT) Population includes all randomized subjects who receive at least 1 dose of IMP and who contribute any efficacy data to the study. The mITT Population will be used for the efficacy analyses based on the treatment they actually received during double-blind treatment phase.

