4.3. Reporting Conventions

The following reporting conventions apply generally to tables, listings, and figures:

- All by-visit summaries and analyses will be provided separately for the double-blind treatment phase and the open-label extension phase, unless otherwise specified. Only subjects who continued to the open-label extension phase will be included in the summaries of open-label extension phase based on the open-label safety populations.

- For subjects who continued into the open-label extension phase, the first dose of IMP at the open-label extension phase will be used as the cutoff date. Since the first dose administration date at the open-label extension phase is not collected electronically, and the dosing schedule is twice/week, either the first IMP kits and equipment dispense date or the next date after completion date of double-blind phase, whichever is the later date, has been used as the best estimate of the first dose of IMP in the open label extension phase. The assessments collected before the cutoff date will be summarized in the double-blind treatment phase and the assessments collected on or after the cutoff date will be summarized in the open-label extension phase, unless specified otherwise. Subjects who did not continue into the open-label extension phase will be summarized in the double-blind treatment phase only.
- Summaries for the double-blind treatment phase will be based on the treatments that the subjects actually received at the double-blind treatment phase. Summaries for the open-label extension phase will also be based on the treatment sequences that the subjects actually received during overall study phase, e.g. Acthar/Acthar and Placebo/Acthar.
- Study Day 1 is defined as the date of the first dose of IMP at the double-blind treatment phase. Study days are calculated as the difference between the date of interest and Study Day 1 plus 1 day. For events before Study Day 1, study days will be calculated as the difference in days between Study Day 1 and the date of interest. The day before the date of the first dose at the double-blind treatment phase will be defined as Day -1. This means there will be no study Day 0.

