4.4.2. Safety Population

The Safety Population includes all randomized subjects who receive at least 1 dose of IMP and will be used for all the safety analyses which will be based on the actual treatment received at the double-blind treatment phase.

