The significant protocol deviations will be summarized by category using frequency tabulations based on the safety population in the double-blind treatment phase and on open-label safety population in the open-label extension phase separately. The cut off of two study phases has been defined in reporting conventions [section 4.3](#). Listings of significant protocol deviations will be provided to support the summary tables.

7. Demographics and Baseline Characteristics

Demographics and baseline characteristics will be summarized by treatment group and total using the mITT population and safety population in the double-blind treatment phase and open-label safety population in the open-label extension phase. Individual subject listings will be provided to support the summary tables for all randomized subjects in the double-blind phase.

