8.3. Study Treatments

Study treatments and extent of exposure summaries will be provided based on the safety population in the double-blind treatment phase and the open-label extension phase, respectively. Descriptive statistics will be provided for treatment duration, number of injections, dose reduction and justifications for dose reduction by study phases.

A listing for each study phase will be provided for drug accountability and treatment compliance, respectively.

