8.3.2. Treatment Compliance

During each visit, the number of injections that a subject was expected to take and the number of injections that a subject actually took since previous visit until prior to the current visit will be recorded on the eCRF.

Treatment compliance (%) of double-blind treatment phase is defined as:

$$\frac{(\text{Number of injections taken during double - blind treatment phase}) \times 100}{\text{Number of injections expected to be taken during double - blind treatment phase}}$$

Treatment compliance (%) of open-label extension phase is defined as:

$$\frac{(\text{Number of injections taken during the duration open - label extension phase }) \times 100}{\text{Number of injections expected to be taken during open - label extension phase}}$$

The study drug compliance rate in the double-blind treatment phase, and compliance rate in the open-label extension phase will be summarized by treatment group using the descriptive statistics. The compliance rates will also be summarized by categories (<80, 80 to <=120, and >120).

9. Efficacy Analysis

All efficacy evaluations will be conducted using the mITT population unless otherwise specified and will be provided by treatment group for the double-blind treatment phase. Efficacy evaluations will only be summarized descriptively using the open-label safety population by treatment group and total for the open-label extension phase. All summaries and analyses will be conducted on the observed values unless otherwise specified. All efficacy data will be presented in listings based on the mITT population in the double-blind treatment phase and based on the open-label safety population in the open-label extension phase. The derived efficacy variables will be displayed in data listings as well.

Additional subgroup analyses by sex, race and ethnicity will be performed on missing imputed data as specified. Other exploratory analyses may be performed as appropriate.

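### Double-blind mITT efficacy is grouped by treatment received, not by randomised arm, and a subject given both products has no defined group

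*SAP*

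**What the plan says.** SAP 4.4.1 defines the mITT population as randomised subjects with at least one dose and some efficacy data, and then fixes the grouping: "The mITT Population will be used for the efficacy analyses based on the treatment they actually received during double-blind treatment phase". SAP 4.3 makes this the general convention: "Summaries for the double-blind treatment phase will be based on the treatments that the subjects actually received at the double-blind treatment phase". SAP 4.4.2 uses the same basis for the safety population, which "will be used for all the safety analyses which will be based on the actual treatment received at the double-blind treatment phase". Efficacy and safety therefore share one as-treated grouping.

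SAP Section 9 adds only this on the analysis set: "All efficacy evaluations will be conducted using the mITT population unless otherwise specified". Results are then given by treatment group, which SAP 4.3 and 4.4.1 have already defined as treatment received. SAP Section 7 uses the mITT population for baseline tables too: "Demographics and baseline characteristics will be summarized by treatment group and total using the mITT population and safety population".

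The protocol (15.2 and 15.5) makes mITT the efficacy set but does not say how subjects are grouped. The SAP therefore does not contradict the protocol.

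**The concern.** Randomisation supports a comparison only when subjects are analysed in the arm to which they were allocated. A population labelled modified intent-to-treat but grouped as treated gives up that support as soon as one subject receives the wrong product. A subject's reclassification would then depend on events after randomisation, such as a dispensing error, and possibly on how long the subject stayed in the study.

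The rule is also incomplete. IMP is dispensed at successive visits (Protocol 11.3) under IXRS assignment (Protocol 12.1.2), so a subject could in principle receive both products during the double-blind phase. Neither SAP 4.4.1 nor 4.4.2 says which group that subject would join. Without a rule fixed in advance, the choice would be made with the data in hand.

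The study is exploratory, so what is at stake is mainly the estimate and its standing as a randomised comparison. Whether a p-value falls on one side of 0.05 matters less.

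**Working it through.** **Does anything else in the plan restore the randomised comparison?**

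- STS sensitivity analysis (SAP 9.1): uses observed data in place of imputed data. The grouping is unchanged.
- All-randomised set (SAP Sections 5 and 7): used for disposition and listings, not for efficacy.
- Changes in the planned analysis (SAP Section 13): grouping is not mentioned.
- Acthar/Acthar and Placebo/Acthar sequences (SAP 4.3, 4.4.3): cover the planned switch at open label, not mixed receipt in the double-blind phase.
- Baseline of active treatment (SAP 4.3): sets a baseline, not an arm.
- Compliance (SAP 8.3.2): compares "the number of injections that a subject was expected to take and the number of injections that a subject actually took". It counts injections and does not identify the product.

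None of these provides an as-randomised efficacy analysis or a rule for mixed receipt.

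**How much can one subject move the result?** The plan states no figure on this point, so there is nothing to reproduce. What follows is an illustration.

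Inputs from the documents: 55 subjects randomised (SAP 4.1); 1:1 allocation (SAP 4.2); two-sided 0.05 (SAP 4.3); Pearson chi-square for STS responders, with Fisher's exact test if any expected count is below 5 (SAP 9.1).

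Assumptions: a 28/27 split, all responder counts, one subject who received the other product throughout, and all 55 in the mITT population. The actual mITT size is not given and may be smaller.

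Formula: difference = a/n − b/m, where a of n respond on Acthar and b of m on placebo. Pearson chi-square is taken without continuity correction.

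As randomised, 15/28 − 8/27 = 53.6% − 29.6% = 23.9 points, p = 0.072. Grouped as treated after one move:

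| Subject who received the other product | Acthar | Placebo | Difference (points) | Shift | p |
|---|---|---|---|---|---|
| Placebo-arm responder | 16/29 | 7/26 | 28.2 | +4.3 | 0.034 |
| Acthar-arm non-responder | 15/27 | 8/28 | 27.0 | +3.0 | 0.043 |
| Placebo-arm non-responder | 15/29 | 8/26 | 21.0 | −3.0 | 0.116 |
| Acthar-arm responder | 14/27 | 9/28 | 19.7 | −4.2 | 0.139 |

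This starting result lies near 0.05, so it shows p-values at their most sensitive. A wider range gives a fairer picture:

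- Acthar 8 to 22 of 28 against placebo 8/27 (15 starting results): the largest shift is 5.2 points, from 8/28 v 8/27 (−1.1) to 9/29 v 7/26 (+4.1). A single move crosses 0.05 from 2 of the 15.
- Placebo also varied from 6 to 12 of 27 (15 × 7 = 105 starting results): the largest shift is 5.5 points, from 8/28 v 6/27 (6.3) to 9/29 v 5/26 (11.8). A single move crosses 0.05 from 15 of the 105, all with a starting p between 0.032 and 0.103.

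The smallest expected count anywhere in the grid is 6.6, so Pearson applies throughout.

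A second set of assumed counts shows that these shifts are not an upper bound. From 17/27 v 10/28 (27.2 points, p = 0.043), moving three placebo-arm non-responders to Acthar gives 17/30 v 10/25 (16.7 points, p = 0.218). Moving three placebo-arm responders gives 20/30 v 7/25 (38.7 points, p = 0.004).

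**The case against.** The strongest reply is that the problem is wholly conditional. Without a wrong-product case the two groupings coincide. None is reported, no misallocation rate is given, and IXRS assignment is a control against cross-dispensing. The study is exploratory, with no formal sample size calculation. All of that stands, and it is why the point is minor. It does not remove the point, because an analysis plan should fix its grouping without relying on no error having occurred.

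A second reply is that dispensing errors could surface in outputs already planned. Deviations are tabulated ("The significant protocol deviations will be summarized by category using frequency tabulations based on the safety population", SAP Section 6), and SAP 8.3 adds: "A listing for each study phase will be provided for drug accountability and treatment compliance, respectively". Protocol 12.5 also requires subject-by-subject accounting of IMP. This is fair: the records may exist. However, no planned output is specified to count wrong-product receipt, and detecting a case would not settle how it is analysed.

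A third reply is that the figures are neither an estimate nor a bound: they rest on assumed counts, one moved subject in the main illustration, and 55 randomised in place of an unknown mITT number. That is correct, and they should be read only as a sense of scale.

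Finally, once efficacy is grouped by randomised arm, a mixed-receipt rule is no longer needed for the main efficacy analysis. It would serve the safety tables and any as-treated sensitivity analysis, so it is a secondary part of the fix.

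**Conclusion.** The concern holds. The SAP states the as-treated grouping for double-blind mITT efficacy outright, plans no as-randomised efficacy analysis, and leaves mixed receipt undefined. The effect is zero if nobody received a wrong product. Otherwise its direction is unknown. Under the assumptions above, one subject wholly on the other product shifts the responder difference by at most 5.5 points across the grid, and more subjects would shift it further. Severity is minor. Confidence in the reading of the text is high; the numbers are illustrative only.

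**What to change.** 1. SAP 4.4.1: state that mITT efficacy is analysed by randomised arm.
2. SAP 4.3: use randomised arm for double-blind mITT efficacy, its listings, and the mITT demographic and baseline tables of Section 7. Keep actual treatment for safety-population summaries.
3. SAP 4.4.2: fix before analysis how actual treatment is assigned when a subject received both products. Counting the subject as Acthar after at least one Acthar dose is one possible rule.
4. Report, by randomised arm, the number of subjects who received any wrong product, drawn where possible from the deviation and drug accountability outputs. Show as-treated efficacy only if that number is above zero, and label it a sensitivity analysis.

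Open-label outputs and plots spanning both phases need no change.

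The cost is wording in three SAP sections, a switch of treatment variable in the double-blind efficacy and mITT baseline programs, and one count. The regrouping needs no new data. The count depends on kit-level or accountability records being available, which the documents do not confirm for the analysis database. If the count is zero, no result changes and the report can say that the comparison is the randomised one.
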